1 PROTOCOL SUMMARY

1.1 SYNOPSIS

Title: PAZAZ: Personalized azithromycin/metronidazole, in combination with standard induction therapy, to achieve a fecal microbiome community structure and metagenome changes associated with sustained remission in pediatric Crohn's Disease (CD)-- a pilot study

Study Description: This is a multi-center, randomized, controlled open-label add-on design trial pilot study to evaluate the efficacy of personalized adjunctive antibiotic (azithromycin + metronidazole) therapy in pediatric subjects with mild to moderate Crohn's disease (CD) who have a relapse-associated microbiome profile. The study hypothesis is that adjunctive antibiotic therapy will improve clinical response to standard of care (SOC) induction therapy in a subgroup of CD patients with a relapse-associated microbiome profile. This is an add-on design trial for subjects already receiving SOC induction therapy; there will be no placebos.

Prior to starting SOC induction therapy at week 0, subjects will provide a baseline stool sample that will be screened for microbiome profiles associated with risk of relapse according to an established statistical model.

At week 4, subjects with a relapse-associated microbiome will be randomized into either a control arm that will continue to receive SOC induction therapy for an additional 8 weeks, or a treatment arm that will receive adjunctive antibiotic therapy in addition to continuing to receive SOC induction therapy for an additional 8 weeks. Subjects who do not have a relapse-associated microbiome will enter a separate control arm that will continue to receive SOC induction therapy and will have data collected for exploratory objectives. Subjects who are not in clinical

remission by week 4 will receive antibiotic therapy regardless of microbiome signature at baseline. Subjects will be monitored for an additional 40 weeks after the treatment period (52 weeks total).

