1.3 SCHEDULE OF ACTIVITIES (SOA)

Procedures	Visit 1 Screening ≤30 days prior to week 0	Visit 2 Week 0	Study Visit 3 Week 4	Study Visit 4 Week 12	Study Visit 5 Week 24	Study Visit 6 Week 36	Final Study Visit 7 Week 52
Informed consent	X						
Demographic data	X						
Medical history	X	X	X	X	X	X	X
Review inclusion/exclusion criteria	X	X					
Concomitant medication review	X	X	X	X	X	X	X
Physical exam (including height and weight)	X	X	X	X	X	X	X
Medication calendar distribution and teaching		X					
Blood sample ^a	X	X ^b	X	X	X	X	X
Calculate PCDAI score (0-100)	X	X ^b	X	X	X	X	X
Stool sample (16S rRNA)	X	X ^b	X	X	X	X	X
Stool sample (FCP)	X	X ^b	X	X	X	X	X
Stool sample (C. difficile infection testing) ^c	X						
Urine pregnancy test ^d	X		X				
Adverse event review and evaluation			X	X	X	X	X
Randomization			X				
ECG, if applicable ^e			X				
Administer antibiotic, if applicable			X				
Teaching for antibiotic medication calendar, if applicable			X				
Complete Case Report Forms (CRFs)	X	X	X	X	X	X	X
IMPACT (ages 9 and older)		X		X	X		X

A window of study timepoint +/- 5 days is allowed for all visits/questionnaires/sampling.

a: Includes hematology and clinical chemistry Albumin, C reactive protein (CRP), hematocrit (HCT), erythrocyte sedimentation rate (ESR), alanine transaminase (ALT), aspartate transaminase (AST), creatinine, and bilirubin. Total blood volume collected at each visit will be 5ml.

b: The timing of the Screening and Week 0 visits will depend on the start of therapy. Week 0 blood and stool samples will not be repeated if provided during the screening visit, provided that the stool samples were collected prior to bowel prep.

c: If performed for clinical indication, as per standard of care

d: Only applicable for post-menarchal female participants initiating methotrexate

Procedures	Visit 1 Screening ≤30 days prior to week 0	Visit 2 Week 0	Study Visit 3 Week 4	Study Visit 4 Week 12	Study Visit 5 Week 24	Study Visit 6 Week 36	Final Study Visit 7 Week 52
e: All patients randomized to group A2 and C will receive an ECG exam both prior to and at 2-4 weeks after the initiation of the study drug							

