2.3.3 ASSESSMENT OF POTENTIAL RISKS AND BENEFITS

The available information suggests that the present clinical study has an acceptable risk-benefit ratio.

Approximately 50% of pediatric patients with CD will relapse within a year of starting induction therapy and require repeated courses of induction therapy and/or treatment escalation.^{41,42} Subjects in the antibiotic treatment arm of this trial will continue to receive standard therapy and are at comparable risk of relapse as subjects in the control arms. In group C of subjects not achieving remission with nutritional induction therapy alone, there will be no randomization and antibiotics will be given as additional induction treatment. The patient, parents and treating physician are free at all times to choose any treatment outside of the study.

The risk of rare, but serious, heart-related side effects from the antibiotic drug azithromycin are minimized by screening patients for heart rhythm irregularities prior to administering antibiotics. Metronidazole presents minimal risk to the subjects and is routinely used in this pediatric population. The safety monitoring practices employed by this protocol are adequate to protect the subjects' safety and detect all anticipated adverse events.

Subjects in the antibiotic intervention arm may experience direct health benefit through the study treatment by reducing their risk of disease flare thus avoiding additional intestinal damage as well as additional immune suppression or surgery. There will be no additional direct benefit for subjects in the reference arms because they will be receiving standard care. The knowledge gained from this trial could lead to improved treatment approaches for a subgroup of patients who have a relapse-associated microbiome profile.

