4 STUDY DESIGN

4.1 OVERALL DESIGN

The primary hypothesis tested is that administering adjunctive antibiotic therapy to patients with a relapse-associated gut microbiome profile will help to sustain clinical response to standard induction therapy for mild to moderately active Crohn's disease.

To test this hypothesis, patients with a relapse-associated microbiome profile will be identified via baseline stool sample analysis and will be randomly allocated to the treatment arm that will receive antibiotics (azithromycin + metronidazole) on top of SOC induction therapy, or a control arm that will receive SOC induction therapy alone. Patients not achieving clinical remission (PCDAI greater than 10 at week 4), can receive antibiotics (azithromycin/metronidazole), will not be randomized, and will continue to be followed until 52 weeks. This pilot trial is intended to be a smaller version of a larger trial, and will be used to evaluate feasibility including standard deviation of the outcome measures, adherence, and baseline microbiome profiling.

Standard of care (SOC) induction therapy, as started by the responsible physician, for this study will be defined as Crohn's Disease Exclusion diet nutritional therapy (CDED Phase 1 from 0-6 weeks and Phase 2 from 6-12 weeks), in accordance with the recently published RCT for the CDED.²⁴

This is a 52-week, multicenter, randomized, controlled, open-label add-on design clinical trial pilot trial to test the feasibility of a larger trial evaluating the efficacy of adjuvant antibiotic therapy in pediatric patients with mild to moderate CD. This study will not be blinded.

A total of 20 subjects between the ages of 3 and 17 years inclusive will be enrolled in eight investigational sites located in Canada, the United States, the Netherlands and Israel.

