Subjects will be stratified based on microbiome profile before they are randomized. A baseline stool sample provided at or within 30 days of week 0 will be processed for DNA sequencing and analyzed by a blinded bioinformatician at Dalhousie University. At week 4, subjects will be assigned to Group A or B based on posterior probability of having a 'relapse-associated' microbiome according to an established statistical model. If patients have not achieved clinical remission, they will be assigned to group C to receive antibiotic for 8 weeks. Subjects in Group A will be randomly assigned to continue SOC therapy alone (Group A1) or to receive add-on antibiotic therapy in addition to SOC (Group A2) for the next 8 weeks (week 4-12). Subjects in Group B will continue on SOC therapy alone for the next 8 weeks.

At week 0, a medication calendar will be distributed to all subjects and patients/families will receive teaching on how to complete it for SOC therapy. At week 4, subjects randomized to Group A2 will be given additional instructions on how to complete the calendar for antibiotic treatment. The calendar will be returned to study staff at week 12 to be used as a measure of compliance and adherence.

Pediatric patients with mild to moderate CD are normally started on an immunomodulator during induction therapy to help maintain remission. Although methotrexate is not FDA approved for this purpose, in this study, subjects will receive 15mg/m² subcutaneous (s.c.) methotrexate (MTX) as maintenance therapy (max. 25mg weekly), consistent with several current international guidelines as standard of care⁴⁶, unless there are contraindications, or oral MTX is preferred and/or the patient/family refuses immunomodulatory therapy.⁴⁷ However, the use of MTX is not a condition to take part in this study. The use of MTX is only prescribed under guidance of the treating physician.

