8.2 SAFETY AND OTHER ASSESSMENTS

Electrocardiograms (ECGs): ECG is for screening purposes only to identify prolongation of QT (QTc) corrected for age appropriate norms. If there is prolongation, as identified by each responsible physician, then the responsible physician is responsible for communicating this finding with the patient and family and arranging appropriate follow-up with cardiology. Patients found to have QT prolongation will not be treated with investigational therapy and appropriate guidance will be given regarding avoiding other medication with the potential of QTc prolongation (e.g. avoiding ondansetron). Further, all patients randomized to group A2 will receive a follow-up ECG 2-4 weeks after the initiation of the study drug to ensure that new-onset QT prolongation is not occurring as a result of azithromycin treatment. If clinically significant QT prolongation is detected at follow-up ECG, patients should discontinue investigational therapy. If the subject is not in clinical remission at week 4, then the responsible physician will decide whether azithromycin/metronidazole can be started as additional induction therapy.

Blood samples: Blood drawn as per the standard of clinical care will be tested for alanine transaminase (ALT), aspartate transaminase (AST), bilirubin, BUN and Creatinine by the local clinical labs to monitor for toxicity due to methotrexate.

Urine pregnancy tests: A urine pregnancy test will be administered at screening and repeated at week 4 prior to the initiation of methotrexate in post-menarcheal female patients. These tests will be used to prevent exposure of participants to potential embryotoxic/teratogenic effects of methotrexate. Counselling and reinforcement of these potential risks and the importance of pregnancy prevention will be included at every study visit. Post-menarcheal patients will be counselled about the use of birth control to prevent unplanned pregnancy while taking methotrexate during this study period.

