9.2 SAMPLE SIZE DETERMINATION

Based on published literature, 50% of children will require repeat induction/treatment escalation by the end of the first year after diagnosis.⁴³⁻⁴⁵ 25 children carrying the high-risk microbiome signature will need to be randomized to each study arm (A1 or A2) (10% drop out assumed) in the larger trial following on from this pilot trial, assuming 80% power, to reduce the risk of flaring from 80% to 40%. These calculations are based on assumptions of relapse risk as no prospective microbiome data are available to inform this risk prediction of an unfavourable disease course.

In this pilot trial, 20 children will be enrolled to assess feasibility. The clinical data about relapse risk were not used to determine this sample size for the pilot trial. The 20 children of the pilot study will be allocated to either group A or group B, based on baseline microbiome data, unless the subject does not achieve clinical remission at week 4. If the subject does not achieve clinical remission (PCDAI less than or equal to 10) then the responsible physician can decide to start azithromycin/metronidazole for 8 weeks as additional induction therapy in Group C. Randomization will determine whether patients in group A, will be given SOC (A1) or SOC+antibiotics (A2).

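### The protocol gives two answers on whether Group C has the on-treatment ECG, and two on whether antibiotics in Group C are required or optional

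*Combined protocol and SAP*

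**What the plan says.** **Follow-up ECG.** Footnote e of the Schedule of Activities (1.3) reads "All patients randomized to group A2 and C will receive an ECG exam both prior to and at 2-4 weeks after the initiation", meaning the start of treatment. Section 8.2 states the follow-up for one group only: "all patients randomized to group A2 will receive a follow-up ECG 2-4 weeks after the initiation of the study drug". It gives the reason as ensuring that azithromycin is not causing new QT prolongation, and its next sentence ties stopping the investigational therapy to a finding on that ECG. The same paragraph opens by saying that "ECG is for screening purposes only to identify prolongation of QT (QTc) corrected for age appropriate norms".

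**Antibiotics for children not in remission at week 4.** The synopsis (1.1) says that subjects not in clinical "remission by week 4 will receive antibiotic therapy regardless of microbiome signature at baseline". Section 2.3.3 says that in Group C "there will be no randomization and antibiotics will be given as additional induction treatment". Section 4.1 contains two statements. One says that these patients "can receive antibiotics (azithromycin/metronidazole), will not be randomized, and will continue to be followed until 52 weeks". The other reads "If patients have not achieved clinical remission, they will be assigned to group C to receive antibiotic for 8 weeks". Section 4.2 says that Group C allows patients to have the additional antibiotic. Section 8.2 leaves it to the responsible physician to decide whether the drugs can be started. Section 9.2 says that "the responsible physician can decide to start azithromycin/metronidazole for 8 weeks as additional induction therapy in Group C".

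**Use of Group C.** Section 9.3 analyses Group C samples as a separate group in an observational arm. The Netherlands addendum (section 12) makes the proportion of patients per treatment arm a feasibility measure. It says the study procedure will have to be redesigned if those proportions depart strongly from what was expected.

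**The concern.** Group C children can take the same azithromycin and metronidazole combination as A2. An ECG done before treatment cannot show prolongation that begins on treatment, and the stopping instruction in 8.2 depends on the later ECG. A site that builds its visit plan from 8.2 would not book that ECG for Group C. A site that builds it from the schedule would. In a trial across four countries, that could mean different safety monitoring of children on the same drug.

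The second inconsistency is about who is in the group. If antibiotics are required, Group C consists of non-remitters assigned to antibiotics. If they are optional, a non-remitter whose physician withholds them is either an untreated member of Group C or belongs to no named group. The observational summary of Group C and the count of patients per arm both depend on which applies.

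**Working it through.** The documents state no figure on this point and no arithmetic decides it. The check is to set the current statements side by side. None of them comes from the amendment log.

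**1. Which groups have the on-treatment ECG?**

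| Place | Before drug start | 2-4 weeks after drug start |
|---|---|---|
| 1.3, footnote e | A2 and C | A2 and C |
| 8.2 | Anyone found to have QT prolongation is not treated; no group named | A2 only |
| 2.3.3 | Rhythm screening before antibiotics; no group named | Not addressed |

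The pre-treatment column is consistent; the last column is not. Two features of the wording add to the confusion:
- 8.2 describes the ECG as for screening only, then orders a follow-up ECG with a different purpose.
- Footnote e speaks of patients randomized to A2 and C, although 2.3.3 and 4.1 both say that Group C is not randomized.

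On timing, a drug start at week 4 puts the follow-up at weeks 4 + 2 = 6 to 4 + 4 = 8. The schedule has no visit between weeks 4 and 12. This is minor, because footnote e already gives the interval.

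**2. Are antibiotics required or optional for non-remitters?**

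| Place | Force of the wording |
|---|---|
| 1.1 Synopsis | Required |
| 2.3.3 | Required |
| 4.1, paragraph on microbiome stratification and group assignment | Required |
| 4.1, paragraph on testing the hypothesis | Optional |
| 4.2 | Permissive |
| 8.2 | Physician decides |
| 9.2 | Physician can decide |

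Three statements read as required and four as optional or permissive. Section 4.1 holds one of each kind, so the conflict is not simply between a summary and a detailed section.

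**3. What follows for the definition of Group C?** Sections 2.3.3 and 4.2 and the group-assignment statement in 4.1 identify the group by failure to reach remission. Section 9.2 can be read as identifying it by the physician's decision to start the drugs. The two definitions select the same children only if every non-remitter is treated. The two issues also meet in footnote e: both of its ECGs are timed from drug initiation, so they have no reference date in a child who never starts.

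**4. Where does it reach the analysis?** The primary comparison is A1 versus A2 (9.3, 9.4.2), and both pooled comparisons in 9.4.3 use only A1, A2 and B. Group C enters neither. It does enter the separate observational analysis in 9.3. An unclear Group C also leaves it unclear how untreated non-remitters count in the per-arm feasibility proportions in section 12.

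**The case against.** The strongest reply on the ECG is that 8.2 omits Group C without excluding it. Footnote e is explicit, is part of the protocol, and can be followed without breaching 8.2. Other protections are not tied to A2: the arrhythmia-risk exclusion in 5.2, the bar in 8.2 on treating anyone with QT prolongation, the screening described in 2.3.3, and new-onset QT prolongation as a withdrawal reason in 7.2. All of this stands. A reader might infer that Group C would take azithromycin with no QT safeguard, and the documents do not support that. What remains is narrower: the safety section names one group and the schedule names two for the same on-treatment test.

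On antibiotics, *will* could state the default and *can* the physician's discretion, especially as 2.3.3 lets patient, parents and physician choose other treatment at any time. That softens the conflict but does not remove it. The two statements in 4.1 still differ, and neither says where an untreated non-remitter is counted.

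A reader might also infer that Group C has no recoverable exposure, or that the efficacy comparison is compromised. Neither follows. Section 6.5 requires concomitant prescription medication, including additional antibiotics, to be recorded on the CRF, so who was treated should be recoverable. Group C is also outside every planned group comparison, and the summary tables in 9.4.1 list only A1, A2 and B.

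**Conclusion.** Both inconsistencies are real and should be resolved, but their reach is limited. The first concerns only the follow-up ECG in Group C children who are treated. The second concerns membership of Group C, and through it the observational summary and the per-arm feasibility proportions. The A1 versus A2 primary comparison is unaffected.

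A reader might want a head count, or might infer that Group C will outnumber A2. The documents give neither a week-4 non-remission rate nor a prevalence of the relapse-associated signature. Any split of the 20 children would be an assumption with nothing in the plan behind it, so no count is offered. The conclusion rests on the wording alone and takes no position on which monitoring or treatment rule is right.

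**What to change.** 1. Reconcile footnote e of 1.3 with 8.2, so that a single statement says which antibiotic-treated groups have the follow-up ECG. Bring the screening-only sentence in 8.2 into line with that statement.
2. Correct footnote e so that it no longer describes Group C as randomized.
3. Reconcile 1.1, 2.3.3, both statements in 4.1, 4.2, 8.2 and 9.2 on whether antibiotics in Group C are required or optional.
4. Define Group C once, saying whether a non-remitter who does not start antibiotics belongs to it. Use that definition in 9.3 and for the per-arm proportions in section 12.
5. If antibiotics are optional, report treated and untreated non-remitters separately.

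The clinical choices in items 1 and 3 are for the sponsor. The cost is an amendment to wording, with the IRB approval that the protocol requires for any amendment, and at most one further split in a descriptive table. Sample size, randomization and the primary analysis do not change.

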8.3 ADVERSE EVENTS AND SERIOUS ADVERSE EVENTS

8.3.1 DEFINITION OF ADVERSE EVENTS (AE)

Adverse event means any untoward medical occurrence associated with the use of an intervention in humans, whether or not considered intervention-related (21 CFR 312.32 (a)).

8.3.2 DEFINITION OF SERIOUS ADVERSE EVENTS (SAE)

An adverse event (AE) or suspected adverse reaction is considered "serious" if, in the view of either the investigator or sponsor, it results in any of the following outcomes: death, a life-threatening adverse event, inpatient hospitalization or prolongation of existing hospitalization, a persistent or significant incapacity or substantial disruption of the ability to conduct normal life functions, or a congenital anomaly/birth defect.

Important medical events that may not result in death, be life-threatening, or require hospitalization may be considered serious when, based upon appropriate medical judgment, they may jeopardize the

participant and may require medical or surgical intervention to prevent one of the outcomes listed in this definition.

8.3.3 CLASSIFICATION OF AN ADVERSE EVENT

8.3.3.1 SEVERITY OF EVENT

For adverse events (AEs) not included in the protocol defined grading system, the following guidelines will be used to describe severity.

- **Mild** – Events require minimal or no treatment and do not interfere with the participant's daily activities.
- **Moderate** – Events result in a low level of inconvenience or concern with the therapeutic measures. Moderate events may cause some interference with functioning.
- **Severe** – Events interrupt a participant's usual daily activity and may require systemic drug therapy or other treatment. Severe events are usually potentially life-threatening or incapacitating. Of note, the term "severe" does not necessarily equate to "serious".

8.3.3.2 RELATIONSHIP TO STUDY INTERVENTION

All adverse events (AEs) must have their relationship to study intervention assessed by the clinician who examines and evaluates the participant based on temporal relationship and his/her clinical judgment. The degree of certainty about causality will be graded using the categories below. In a clinical trial, the study product must always be suspect.

- **Related** – The AE is known to occur with the study intervention, there is a reasonable possibility that the study intervention caused the AE, or there is a temporal relationship between the study intervention and event. Reasonable possibility means that there is evidence to suggest a causal relationship between the study intervention and the AE.
- **Not Related** – There is not a reasonable possibility that the administration of the study intervention caused the event, there is no temporal relationship between the study intervention and event onset, or an alternate etiology has been established.

